### 3.3 Data Collection

The main data source within the RSAR will be an electronic database of patients developed on the basis of the "Medical online platform ROSMED.INFO", which is the own development of LLC "RSMI".

The attending physicians of patients with SA will enter information online in the electronic database. As investigation centers will be used health facilities of federal and regional levels, which include specialized pulmonological and allergic departments. These centers have the opportunity to include the largest number of patients with SA in the study, and they also have extensive experience in the management and monitoring of such patients. The total number of health facilities is 100. The centers participating in the study will collect data on all patients diagnosed with SA who have signed written informed consent to participate in the study. Data collection will be carried out on a regular basis during routine patient visits to a doctor or in case of hospitalization. In the work period of this project, no special additional procedures for collecting information will be used. The information will be collected from outpatient cards and / or case histories, based on data received by the physician during routine examination of the patient. Visitors of [www.rosmed.info](http://www.rosmed.info) site can not participate in the RSAR study without first being invited by the attending physician.

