### 3.5. Inclusion Criteria

- Patients aged 12 years or older.  
Patients with confirmed diagnosis of severe asthma.
- Patients receiving treatment according to GINA step 5 or uncontrolled for 4 step. Uncontrolled patients are defined as having symptoms of severe asthma or frequent exacerbations.  
Signed informed consent.

---

 Severe symptoms of BA (Guideline of European Respiratory Society (ERS)/American Thoracic Society (ATS)) (2):

(a) BA with uncontrolled symptoms; ACT < 20, ACQ > 1,5;

(b) Limited air-flow rate, for example: FEV1 < 80 % of the norm (along with FEV1/FES at the lower limit of the norm or less) after wash-out period from the bronchodilators;

(c) Severe exacerbation and hospitalization, being in the ICU or on the mechanical ventilation of lungs over the past year.

 Frequent severe exacerbations of BA (guidelines ERS/ATS) (2):

Frequent severe exacerbations of BA (2 or more courses of systemic glucocorticoids over the past year).

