#### **4.4. Statistics analysis**

Primary and secondary statistical indicators will be presented using descriptive statistics methods. Qualitative variables will be presented in the form of incidence and percentage. The quantitative variables will be represented by numerical values, standard deviation indicators, minima and maxima, median and interquartile range. The frequency and severity of adverse events / reactions will be documented according to the Medical Dictionary of Regulatory Terminology, version 16.1. When analyzing the outcome of the disease among patients on therapy (drug), statistical analysis will be performed in a subgroup of newly identified patients. Evaluation of the outcome of SA can be determined by achieving a sufficient number of patients in a subgroup of newly identified patients and patients undergoing therapy (SA). The lack of comparison between groups of patients is due to the inaccuracy of these therapies in the history and treatment approaches.

In the course of the analysis, the standard statistical characteristics of morbidity, prevalence of the disease (SA) and their dependence on the basic demographic indicators (sex, age) will be assessed. The statistical analysis of the endpoints will be performed for patients with a diagnosis period of no more than 6 months from the date of inclusion in the register (a subgroup of newly identified patients) and also when the required amount of statistical data is collected within the register database.

The analysis will use standard methods of descriptive, frequency, logistic statistical analysis.

Hypotheses of the study. The main goal of the study is to obtain statistical estimates of the target epidemiological characteristics, formally asking questions about hypotheses of the study in this case is not applicable. After receiving the estimates, they are expected to be compared with similar ones, known in the foreign and domestic literature and official statistics.

Within the Registry, measures should be taken to collect data on the maximum number of patients within the claimed sample. In the absence of information within the fields of the individual registration card, the validating authority should separate information on the statuses "negative value", "no data", "not investigated".

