#### **4.5. Main analysis.**

The aggregate statistics for continuous variables will include the number of observations (N), the mean value, the standard deviation (SD), the minimum value, Q1 (25th percentile), median, Q3 (75th percentile), maximum value, interquartile range. Tables of categorical variables will represent all possible categories and will display the number of observations for each category, as well as percentages. Precision for percent is one decimal point, if the denominator is less than 100 (in all columns), in this case, percentages are indicated by integers. In general, the percentages will be calculated based on the total number of patients in the analyzed population, regardless of

whether they have missing values or not. The category "Missing" will be displayed when at least one patient falls into this category. The CRF contains several nested questions (that is, questions that require more detailed information only in a subset of patients with a specific value for another question, "if yes" questions); for these variables, percentages will be based on patients with a corresponding value for a higher-level issue, rather than using all patients in the population as reference values.

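### Section 4.4 plans prevalence and morbidity of severe asthma by sex and age, which a registry of confirmed cases with no population denominator cannot validly estimate

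*Combined protocol and SAP*

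**What the plan says.** Section 4.4 states without condition that "the standard statistical characteristics of morbidity, prevalence of the disease (SA) and their dependence on the basic demographic indicators (sex, age) will be assessed". It defines neither morbidity nor prevalence and names no denominator. Of the study's estimates in general it adds that "they are expected to be compared with similar ones, known in the foreign and domestic literature and official statistics", without saying which estimates are meant. The methods are described broadly: "Qualitative variables will be presented in the form of incidence and percentage", and "The analysis will use standard methods of descriptive, frequency, logistic statistical analysis".

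Section 4.5 gives the general rule that "the percentages will be calculated based on the total number of patients in the analyzed population"; nested questions use subsets of that population.

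Entry is set out elsewhere:
- Section 3.5 requires "Patients with confirmed diagnosis of severe asthma" and "Patients aged 12 years or older".
- Section 3.3 has the centres record "all patients diagnosed with SA who have signed written informed consent to participate in the study", at 100 facilities with specialised departments.
- Section 3.6 excludes intermittent, mild and moderate asthma, and several other diseases.
- Section 4.8 leaves out participants in interventional trials.
- Section 3.1 sets a target of up to 7,000 patients.

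The objectives in 2.1 and 2.2 contain no prevalence or incidence of SA. Age and sex appear there only as characteristics of registered patients.

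**The concern.** Prevalence and incidence need a population that contains people without the disease. This registry contains cases only. Because milder asthma is excluded, even the share of SA among asthma patients is out of reach.

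The population reading of the sentence is plausible. Section 1.1 treats the true incidence of SA as an open question, and 4.4 describes the main goal as estimating epidemiological characteristics. At stake is a count of registered patients, shaped by consent, choice of centres and a recruitment target, being reported as prevalence by sex and age and set beside official statistics that measure something else.

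**Working it through.** **1. The one case count in the plan.** The yearly targets in section 3.2 are 2000 + 2000 + 1000 + 1000 + 1000 = 7000, which matches the target in 3.1. This is a recruitment target, not a count of cases in a defined population.

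**2. What the measures need and what the documents supply.** For sex or age group k:

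- Prevalence = cases in k at a reference date / population in k.
- Incidence = new cases in k / person-time at risk in k.

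| Ingredient | In the documents |
|---|---|
| Cases in k | Registered, consenting cases at participating facilities (3.3, 3.5) |
| Population in k | Not given |
| Person-time at risk of developing SA | Not given; follow-up from 03.2018 to 11.2022 covers people who already have SA (3.1) |
| Population coverage | Not given; 4.8 states only an intention to include all eligible patients |

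Follow-up of registered patients does support event rates within the registry, such as exacerbations. It does not support incidence of SA.

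**3. Using the denominator of section 4.5.** If n patients are registered in group k, the share with SA is n/n = 100% in every group, and every sex or age ratio is 1.00. This assumes no incorrect inclusions. It only restates the entry criterion.

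**4. Using an external denominator.** Let c be the fraction of true cases that the registry captures in a group. Then registered patients per head = c × true prevalence, and the observed female:male ratio = (c for women / c for men) × the true ratio. The documents give no c, so neither level nor pattern can be recovered.

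The figures below illustrate this. Populations, coverages and sex split are assumptions, not document figures.

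- Level: 7000 / (coverage × population). With 120 million people and 100% coverage this is 5.8 per 100,000. With 10 million and 10% coverage it is 700 per 100,000.
- Pattern: assume 65% women (4550 women, 2450 men) and equal male and female populations. The observed ratio is 4550/2450 = 1.86. The true ratio it would correspond to is:

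| Coverage, women / men | True female:male ratio |
|---|---|
| Equal | 1.86 |
| 60% / 30% | (4550/0.6)/(2450/0.3) = 0.93 |
| 30% / 60% | (4550/0.3)/(2450/0.6) = 3.71 |

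These numbers show only that the answer depends on coverage. They do not estimate the error in this registry.

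**5. Using a within-registry reading.** The age and sex distribution of registered patients can be computed. So can the split between newly identified patients (diagnosis within 6 months of inclusion, section 4.4) and existing ones. Both are case mix, not prevalence of SA.

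**The case against.** The best defence is that the sentence is loosely worded. The text reads like a rough translation, and 4.4 also applies the word incidence to simple counts of qualitative variables. Next to the disputed sentence, 4.4 defines a subgroup of newly identified patients, so the authors may have meant newly identified versus existing registered cases by sex and age. That analysis is feasible. The point stands as far as it goes: the population reading is plausible but not certain. It does not rescue the term, since SA does not vary among registered patients.

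A second defence is that ascertainment is addressed. Section 3.1 plans sequential inclusion, and 4.8 intends every eligible patient to be included, with a screening log at each base. This is a real strength at site level. It concerns patients seen at participating bases and supplies no population coverage.

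Third, section 1.2 sets the precedent registry's 519 patients against about 1000 expected from epidemiology, treating the registered count as case detection and not as prevalence. That makes misuse here less likely, though 4.4 does not rule it out.

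A reader might infer stronger things that the documents do not support:
- That the plan will produce a table of 100% prevalence, or a logistic model of SA on sex and age that cannot be fitted. Nothing says that SA status will be tabulated or modelled as an outcome; logistic analysis appears only in a separate, general sentence.
- That the registry's main results are compromised. The objectives in 2.1 and 2.2 are within-registry quantities.
- That the direction or size of a prevalence error is known. It is not.

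**Conclusion.** The concern holds in a limited form. The design cannot validly estimate population prevalence or incidence of SA, or how they vary with sex and age, because it records only selected confirmed cases and the plan names no population, at-risk person-time or coverage. On the looser reading the analysis is feasible but misnamed. The sentence needs changing under either reading.

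The size of any error cannot be quantified from the documents. The primary and secondary objectives, and percentages within the registry generally, are unaffected. The conclusion rests on the documents containing no population denominator, and none was found; it does not depend on the illustrative values. The sentence should be corrected, but it does not threaten the study's main results.

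**What to change.** In section 4.4, replace the phrase on morbidity and prevalence with: 'distribution of registered SA patients (overall and newly identified) by age and sex, and of exacerbations, control, phenotype and treatment within these strata'. In the same section, limit the comparison with literature and official statistics to these within-registry characteristics, and state that it does not extend to population prevalence or incidence.

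The cost is the rewording of two sentences. No new data are needed: age and sex are already collected (section 9, Appendix) and are already secondary objectives, and 2.2 already allows subgroups. No listed objective is lost. The downside is that the registry gives up a population-prevalence claim, which this design cannot support.

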### 2.1. Primary Objective(s)

The key objective of establishing the RSAR initiative is to:

- Percentage of patients with severe asthma according **frequency of exacerbations** (1, 2,  $\geq 3$  exacerbations) at the time of study enrollment;

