### 2.2. Secondary Objective(s)

For the overall sample and by subgroups as appropriate, the secondary objectives are to:

- Percentage of patients with severe asthma according **frequency of exacerbations** (1, 2,  $\geq 3$  exacerbations) at the 1 year of follow-up;
- Percentage of patients with severe asthma according frequency of exacerbations (1, 2,  $\geq 3$  exacerbations) at the 2 year of follow-up;
- Percentage of patients with severe asthma according frequency of exacerbations (1, 2,  $\geq 3$  exacerbations) at the 3 year of follow-up;
- Percentage of patients with severe asthma according frequency of exacerbations (1, 2,  $\geq 3$  exacerbations) at the 4 year of follow-up;

- Percentage of patients with severe asthma according **concomitant diseases** (number of observations, the mean value, the standard deviation) at the time of study enrollment;
- Percentage of patients with severe asthma according concomitant diseases (number of observations, the mean value, the standard deviation) at the 1 year of follow-up;
- Percentage of patients with severe asthma according concomitant diseases (number of observations, the mean value, the standard deviation) at the 2 year of follow-up;
- Percentage of patients with severe asthma according concomitant diseases (number of observations, the mean value, the standard deviation) at the 3 year of follow-up;
- Percentage of patients with severe asthma according concomitant diseases (number of observations, the mean value, the standard deviation) at the 4 year of follow-up;
- Percentage of patients with severe asthma according to parameters: **age** (the mean value, the standard deviation) at the time of study enrollment;
- Percentage of patients with severe asthma according to parameters: **sex** at the time of study enrollment;
- Percentage of patients with severe asthma with different phenotypes in terms of parameters: **IgE (IU/ml)** (the mean value, the standard deviation, the minimum value, median, maximum value) at the time of enrollment;
- Percentage of patients with severe asthma with different phenotypes in terms of parameters: IgE (IU/ml) (the mean value, the standard deviation, the minimum value, median, maximum value) at the 1 years of follow-up;
- Percentage of patients with severe asthma with different phenotypes in terms of parameters: IgE (IU/ml) (the mean value, the standard deviation, the minimum value, median, maximum value) at the 2 years of follow-up;

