#### **4.8. Limitations of study methods.**

The following errors must be taken into account when planning methods for recruiting patients and their follow-up observation:

- Wrong information;
- Incorrect inclusion of the patient in the study;
- Errors in the periods of entering information;
- Removal of the patient at the stage of the beginning of the period of dynamic observation.

In order to reduce the likelihood of these errors within the QMS (quality management system), it is planned to conduct audits for compliance of the RSAR data with the study protocol, the requirements of the study organizers and the legislation of the Russian Federation. The program includes built-in internal validation tools for the entered data. To minimize the risks of mistaken inclusion of patients, the process of registration of patients in the study will be extremely consistent. All patients who meet the inclusion criteria, regardless of location (research base) will necessarily be included in the RSAR. Patients participating in interventional clinical trials will not be included. For the entire population entered in the RSAR, the initial characteristics (primary endpoints) will be examined and analyzed. At each base included in the study, a patient screening log will be kept, including information on the field, age, date of birth, the date of diagnosis of AE of serious gravity, the reason for including the patient / reason for not including the patient in the register, the date of signing the informed consent form for participation in the research, reasons for refusing to participate in the register.

The study monitors will have the opportunity to check the sequence of patients' inclusion in the study. The investigators and organizers of the RSAR will make every effort to minimize unreasonable drop-out of patients from the register, within which regular contact will be made with the patient / his legal representative, in case of dropout, the cause will necessarily be established (with documentary evidence, about death). A signal for an emergency contact with the patient / legal representative will be the miss of another planned visit within the framework of the visit. The contact form and its result will be registered in accordance with the established procedure (SOP LLC RSMI).

In order to minimize the dropout of patients, the following efforts will be made:

- Work with databases where patients are recruited;

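### Read literally, section 4.4 confines the endpoint analysis to patients diagnosed within 6 months of inclusion, which conflicts with the whole-registry population in sections 4.8 and 2.2

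*Combined protocol and SAP*

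**What the plan says.** Section 4.4 contains two statements about recently diagnosed patients.

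- Its opening paragraph concerns disease outcome in patients on therapy, for which "statistical analysis will be performed in a subgroup of newly identified patients". It adds a condition: "Evaluation of the outcome of SA can be determined by achieving a sufficient number of patients in a subgroup of newly identified patients" and in patients undergoing therapy.
- A later paragraph, following a sentence on morbidity and prevalence by sex and age, is general: "The statistical analysis of the endpoints will be performed for patients with a diagnosis period of no more than 6 months", counted relative to inclusion. Its second half reads: "and also when the required amount of statistical data is collected within the register database". It does not separate primary from secondary endpoints, and it does not mention therapy.

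Other sections point elsewhere.

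- Section 4.8: "For the entire population entered in the RSAR, the initial characteristics (primary endpoints) will be examined and analyzed".
- Section 2.2 opens: "For the overall sample and by subgroups as appropriate, the secondary objectives are to". The list that follows covers enrollment and years 1 to 4.
- Section 2.1 sets the primary objective as the percentage of patients by number of exacerbations (1, 2, 3 or more) at enrollment, with no condition on time since diagnosis.
- The last paragraph of 4.4 lets patients who drop out count towards the primary points, again with no 6-month condition.
- Section 4.5 bases percentages on all patients in the analyzed population, including those with missing values. It does not name that population.

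**The concern.** The primary endpoint is a percentage, so its denominator is part of its definition. Section 4.4 is where an analyst looks for the population, and its one general sentence on the endpoints gives a restricted one. The whole-registry statement stands in a section on limitations.

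The second half of the 4.4 sentence does not repair this. It may add an analysis of the full database, or it may set the time at which an analysis is done. It states no amount. The milestones list ten analytic reports (two a year for five years), so an undefined threshold could be applied differently from one report to the next.

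Two things are at stake. One is precision, because the subgroup is smaller. The other is what the percentage describes. Item 19 of the Appendix counts exacerbations over the last 12 months; for a patient diagnosed no more than 6 months before inclusion, at least half of that window precedes the diagnosis. Section 4.4 intends the estimates to be compared with the literature and official statistics, so the population must be clear.

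**Working it through.** **1. The plan's own total.** Yearly targets in section 3.2: 2,000 + 2,000 + 1,000 + 1,000 + 1,000 = 7,000. This matches the target in 3.1 and 3.4.

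**2. Is the 6-month group smaller than the registry?** Section 3.3 has centres collect data on all consenting patients diagnosed with severe asthma, and the criteria in 3.5 and 3.6 set no limit on time since diagnosis. The group is therefore only a part of the registry. No section gives its share.

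**3. Which population do the passages support?**

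- Enrollment endpoint: 4.8 names the primary endpoints and assigns them to everyone entered. Section 2.1 and the dropout paragraph of 4.4 set no 6-month limit. Only the general 4.4 sentence points to the subgroup.
- Year 1 to 4 objectives: 2.2 uses the overall sample, with subgroups in addition. The general 4.4 sentence would use the subgroup.

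**4. Precision, illustration only.** The 95% half-width in percentage points, at a true percentage of 50%, is 196 × √(0.25/n).

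- All 7,000: 1.17.
- Assumed share 30%, n = 2,100: 2.14.
- Assumed share 20%, n = 1,400: 2.62.
- Assumed share 10%, n = 700: 3.70.
- Assumed share 5%, n = 350: 5.24.

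The half-width is multiplied by 1/√share, that is 1.83 at 30% and 4.47 at 5%.

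**5. Shift of the estimate, illustration only.** Suppose that 10% of patients are newly diagnosed, and that 20% of them and 40% of the rest fall in a given exacerbation category. The subgroup figure is 20%. The whole-registry figure is 0.10 × 20 + 0.90 × 40 = 38%. If the two groups do not differ, nothing shifts.

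**6. Can everyone entered serve as the denominator at every time point?** Section 3.1 ends both inclusion and observation in 11.2022. By the targets in 3.2, the patients who cannot reach a given year number at least:

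- Year 1: 1,000 of 7,000 (14%), those planned for 2022.
- Year 2: 2,000 of 7,000 (29%), those planned for 2021 to 2022.
- Year 3: 3,000 of 7,000 (43%), those planned for 2020 to 2022.
- Year 4: 5,000 of 7,000 (71%), those planned for 2019 to 2022.

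Under the 4.5 rule all of these would be counted as missing, by design. Everyone entered is therefore a sound denominator at enrollment but not at follow-up.

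**The case against.** The strongest reply is that the plan, read as a whole, already settles the matter. Section 4.8 speaks to the primary endpoints by name. Section 4.4 calls its own group a subgroup, which presupposes a larger main population, and its opening paragraph links that subgroup to outcome on therapy. Section 2.2 allows subgroup reporting, and the joining words in the 4.4 sentence can be read as additive.

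Much of this stands. A reader might infer that the primary population is left open, or that the plan means the primary result to rest on newly diagnosed patients. The documents do not support either inference: sections 2.1 and 4.8 and the dropout paragraph of 4.4 all point to the whole registry. What does not follow is that the 4.4 sentence is harmless. Nothing in it limits it to therapy outcomes, and subgroup reporting under 2.2 comes in addition to the overall sample, not in place of it.

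It is also fair to object that the share is assumed and that neither 4.4 nor 4.5 plans confidence intervals. The half-widths above show scale only.

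A reader might further infer from the Appendix that the 6-month group cannot be formed, because the printed variables show age at symptom onset but no diagnosis date. That is not established. The screening log in 4.8 appears to record such a date, 5.2 describes an extended variable list, and the printed list may be incomplete. How patients followed in other registries are counted is a separate question.

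**Conclusion.** The conflict is real, and it lies in one sentence. Section 4.4 states a rule for the endpoints that contradicts 4.8 on the primary endpoints and 2.2 on the secondary objectives. The intended population for the enrollment endpoint is reasonably clear, namely the whole registry. The fault is that a literal reading of 4.4 leads to a different denominator and fewer patients.

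The effect cannot be sized from the documents. They give no newly diagnosed share, no precision target that could be breached, and no evidence on whether the two groups differ in exacerbations. The half-widths of 5.2 to 2.1 points against 1.2 rest on an assumed 5% to 30% share, full recruitment of 7,000 and a percentage of 50%. The correction should be made because it is cheap and concerns the primary denominator. It is not evidence that any result is wrong.

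**What to change.** 1. Rewrite the general 4.4 sentence so that the primary endpoint and the other enrollment characteristics are analysed in everyone entered in the registry, as 4.8 says. Name that set in 4.5 as the analyzed population for enrollment tables.
2. State that the year 1 to 4 secondary objectives are analysed in the overall sample, not only in newly identified patients. At each year, the denominator is the patients enrolled early enough to reach that year by the end of observation (11.2022). Those who could not reach it are then not counted as missing.
3. Keep the 6-month group as an additional subgroup for the outcome-on-therapy analyses that 4.4 already assigns to it.
4. Remove the required amount of data as something that determines the population.

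The cost is a short rewording of 4.4 and 4.5, and a smaller stated denominator in the later follow-up tables: on the planned recruitment, at most 7,000 − 5,000 = 2,000 patients at year 4.

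### The plan aims to estimate and compare with published figures but specifies no confidence intervals and ignores clustering in 100 facilities, so differences of a few points cannot be reliably judged

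*Combined protocol and SAP*

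**What the plan says.** Section 4.4 states the aim: "The main goal of the study is to obtain statistical estimates of the target epidemiological characteristics". It treats formal hypotheses as not applicable and describes the next step: "After receiving the estimates, they are expected to be compared with similar ones, known in the foreign and domestic literature and official statistics". It gives no method or criterion for that comparison.

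The primary indicator in Section 2.1 is a set of percentages, by number of exacerbations (1, 2, 3 or more) at enrolment. On output, Section 4.4 says: "Primary and secondary statistical indicators will be presented using descriptive statistics methods". Section 4.5 gives the detail. For continuous data: "The aggregate statistics for continuous variables will include the number of observations (N), the mean value, the standard deviation (SD), the minimum value", followed by the quartiles, median, maximum and interquartile range. For categorical data: "Tables of categorical variables will represent all possible categories and will display the number of observations for each category, as well as percentages". Section 4.5 also sets the number of decimals for percentages. No confidence interval, standard error or confidence level appears anywhere in the document.

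On the source of patients, Section 3.3 says: "The total number of health facilities is 100". Section 3.2 places these facilities in 30 cities. The analysis sections contain no facility effect, design effect, robust variance or table of results by facility. Section 5.1 compares centres, but only as a data-quality check.

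**The concern.** Where no test is planned and the product is a set of estimates to be set beside other estimates, the interval carries the inference. Without it, a registry percentage and a published percentage are compared as if both were exact.

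Clustering makes this worse. The facilities are of federal and regional level, they enrol outpatients and inpatients (Section 3.1), and attending physicians enter data from routine records. Exacerbation frequency can therefore differ between facilities through case mix and through recording. If it does, a simple binomial interval added later from N and the percentage would be too narrow. The planned tables would not let a reader correct it, because they give neither the ICC nor results by facility. A gap of 2 or 3 points could then be reported as a national difference when it is compatible with variation between facilities.

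**Working it through.** **The plan's own figure.** The yearly targets in Section 3.2 sum to 2,000 + 2,000 + 1,000 + 1,000 + 1,000 = 7,000, which agrees with the target in Section 3.1. That target has no stated precision, confidence level or expected percentage behind it, so it cannot be reproduced as a statistical sample size.

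**Inputs from the documents.** N = 7,000 (an upper limit) and 100 facilities, so m = 7,000/100 = 70 if facilities are equal in size.

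**Assumptions.** p = 50%, which gives the widest interval; ICC 0.01 to 0.10; 95% confidence.

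**Formulas.** Design effect DE = 1 + (m − 1) × ICC = 1 + 69 × ICC. Effective n = 7,000/DE. Half-width = 1.96 × √(0.25/7,000 × DE). Actual coverage of a simple 95% interval = 2Φ(1.96/√DE) − 1.

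| ICC | DE | Effective n | Half-width (points) | Coverage of simple interval |
|---|---|---|---|---|
| 0 | 1.00 | 7,000 | 1.17 | 95% |
| 0.01 | 1.69 | 4,142 | 1.52 | 86.8% |
| 0.05 | 4.45 | 1,573 | 2.47 | 64.7% |
| 0.10 | 7.90 | 886 | 3.29 | 51.4% |

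**At what ICC does a gap fall within noise?** Against a published figure treated as exact, set the half-width equal to the gap d and solve: DE = (d/1.96)² × 7,000/0.25.
- d = 0.02: DE = 2.92, so ICC = 1.92/69 ≈ 0.028.
- d = 0.03: DE = 6.56, so ICC = 5.56/69 ≈ 0.081.

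**Unequal facilities.** With an assumed coefficient of variation of facility size of 0.8, DE = 1 + (1.64 × 70 − 1) × ICC. The half-width is 1.71 points at ICC 0.01 and 4.12 points at ICC 0.10.

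**Smaller samples.** At the 2,000 patients planned for 2018 (m = 20), the half-width is 2.19 points without clustering and 2.39, 3.06 and 3.73 points at ICC 0.01, 0.05 and 0.10. If the newly identified subgroup of Section 4.4 were 10% of the total (assumed; 700 patients, m = 7), it is 3.70 points without clustering and 3.81 to 4.69 points for ICC 0.01 to 0.10.

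**Sampling error of the comparator.** Section 1.1 describes a domestic study of 1,000 patients with 42% uncontrolled. Take the registry percentage near 42% and ignore the study's own clustering. The margin for the difference is 1.96 × √(0.42 × 0.58/1,000 + 0.42 × 0.58/7,000 × DE). This is 3.27 points with no clustering, and 3.41, 3.91 and 4.46 points at ICC 0.01, 0.05 and 0.10.

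**The case against.** The strongest reply is that this is a descriptive registry with no hypothesis, no group comparison and no decision rule. The external comparison is one sentence that claims no statistical difference, and intervals could be added at reporting without any change to design or data collection. That limits the seriousness of the point but does not remove it: descriptive estimates still have sampling error, and the plan itself commits to comparing them.

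Three stronger readings are tempting, and the documents do not support them.
- A reader might infer that differences cannot be judged at all. Section 4.5 requires N with percentages, and N with mean and SD, so a simple interval can be derived. In the full sample, gaps well above 5 points exceed sampling error across the ICC range considered.
- A reader might infer that intervals are ruled out. The output list in Section 4.5 is not worded as exclusive, Section 4.4 also names logistic analysis, and Section 5.3 foresees customised analyses. Intervals are unspecified, not excluded. The logistic analysis has no stated model or facility term, however, and would not by itself supply intervals for the primary percentages.
- A reader might infer that any gap of 2 to 3 points is facility noise. At ICC 0.01 the half-width is 1.52 points and both gaps lie outside it.

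Two further objections stand. In the one domestic comparison that the document describes, the comparator's size dominates: 3.27 points before any clustering. In small subgroups the clustering effect shrinks, because there are few patients per facility (DE 1.06 to 1.60 with 7 per facility).

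**Conclusion.** The point holds in limited form. The plan sets estimation and external comparison as its purpose but specifies only point summaries and measures of spread, with no interval and no allowance for facility. Differences of a few points therefore cannot be reliably judged, and a cluster-valid interval cannot be rebuilt from the planned tables.

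For a percentage near 50% in 7,000 patients, precision is between ±1.17 points (no clustering) and ±3.29 points (ICC 0.10, equal facilities). These figures rest on the full target being reached and on an assumed ICC range that the documents neither give nor exclude. The same omission affects the early reports and subgroups, where intervals are wider in any case.

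Intervals would not settle every comparison. Section 3.3 chooses facilities with specialised departments, so they are not a random sample, and the domestic study in Section 1.1 assessed asthma patients at outpatient clinics, not a severe-asthma population. A difference outside sampling error could still reflect case mix or the choice of centres.

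**What to change.** Add to Section 4.5:
- 95% confidence intervals for the primary percentages and the main secondary percentages and means, with facility as the cluster (cluster-robust variance or a bootstrap that resamples facilities), and the estimated ICC for each.

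Add to Section 4.4:
- the published sources to be used as comparators and how a difference will be judged, including the sampling error of the published figure as well as that of the registry;
- a statement that the intervals do not correct for case mix or for the selection of specialised centres.

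The cost is a few lines of text and code. No new data are needed, provided that facility is identifiable in the database. The downside is that stated precision will look less favourable than with a simple interval.
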